**Table 1: Planned Age Groups and mRNA-1273 Dose Levels in Part 1 and Part 2, and Part 3 of the Study**

| Age Group             | Part 1                        |                     |                     | Part 2  |                              | mRNA-1273
25 µg
2 doses of
primary
series +a third
dose
(Month 0, 1,
5) |
|-----------------------|-------------------------------|---------------------|---------------------|---|------------------------------|--|
|                       | mRNA-1273
25 µg            | mRNA-1273
50 µg  | mRNA-1273
100 µg | Selected Dose
Level of mRNA-1273 From Part 1 | Placebo                      |  |
| 6 years to < 12 years |                               | Study Arm 1 (n=375) | Study Arm 2 (n=375) | Study Arm 8 (n=3,000)                           | Study Arm 9 (n=1,000)        | Study Arm 14 (n= approximately 300)  |
| 2 years to < 6 years  | Study Arm 7 (Optional) (n=75) | Study Arm 3 (n=75)  | Study Arm 4 (n=75)  | Study Arm 10 (n=up to 3,000)                    | Study Arm 11 (n=up to 1,000) |  |
| 6 months to < 2 years | Study Arm 5 (n=150)           | Study Arm 6 (n=150) |                     | Study Arm 12 (n=up to 3,000)                    | Study Arm 13 (n=up to 1,000) |  |

Note: mRNA = messenger RNA.

1. Four months post-Dose 2  $\pm$  28 days (at least 3 months and up to 5 months after Dose 2)

The study will begin with the oldest age group (6 years to < 12 years) and age de-escalate. Each age group will begin with Part 1 and may advance to Part 2 and Part 3 independently. The mRNA-1273 investigational vaccine or placebo will be administered as 2 intramuscular (IM) injections, approximately 28 days apart for Part 1 and Part 2. For Part 3, the mRNA-1273 investigational vaccine will be administered as 3 IM injections approximately 28 days apart for the 2 doses of primary series followed by a third dose at least 3 months and up to 5 months after receipt of the second dose of the primary series. The mRNA-1273 dose levels that will be evaluated in each age group in Part 1, Part 2 and Part 3 of the study are given in Table 1.

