## 6.5. Efficacy Analysis

Efficacy analyses will be performed using the FAS, mITT, mITT1 and PP Set for Efficacy. The mITT1 Set will be the primary analysis set used for efficacy analysis of efficacy endpoints starting from 14 days after first dose, and PP Set for Efficacy will be the primary analysis set used in the efficacy analyses for efficacy endpoints starting 14 days after second dose, unless otherwise specified. Subjects will be included in the treatment group to which they were randomized.

**Baseline SARS-CoV-2 status** is described in [Section 6.1](#). Baseline SARS-CoV-2 status, the serology test results at baseline, the RT-PCR test results at baseline will be summarized by age group and treatment group.

Participants with baseline positive or missing SARS-CoV-2 status will be excluded from the PP Set for Efficacy Analysis.

In this study, the serology test results and the RT-PCR test results will be summarized by visit.

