**Table 3. Derivation for SARS-CoV-2 Infection**

| Baseline SARS-CoV-2 Status | Post-baseline assessments |  | Endpoint: SARS-CoV-2 infection |
|-----------------------------------|----------------------------------|--|---------------------------------------|
|                                   | PCR test post baseline           | bAb levels against SARS-CoV-2 Nucleocapsid |                                       |
|                                   |                                  |  |                                       |

|                      |   |      |
|----------------------|---|------|
| Negative at Baseline | Positive (either at nasal swab test, or at symptom-prompt nasal swab test)     | Case |
| Negative at Baseline | Positive (at Post baseline visit or later) as measured by Roche Elecsys | Case |

The date of documented infection will be the earlier of:

- Date of positive post-baseline RT-PCR result, or
- Date of positive serology test result based on bAb specific to SARS-CoV-2 nucleocapsid

The time to the first SARS-CoV-2 infection will be calculated as:

Time to the 1st SARS-CoV-2 infection = Date of the 1st documented infection – Date of randomization + 1. (For Part 1, switch date of randomization to date of 1st injection)

Cases will be counted starting 14 days after the second injection, i.e. date of documented infection – Date of the 2nd injection  $\geq$  14.

SARS-CoV-2 infection cases will also be summarized based on tests performed at least 14 days after first dose.

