**Table 4. Derivation for CDC Case Definition of COVID-19**

|                           | COVID-19   |
|---------------------------|---|
| Post-baseline PCR results | Positive, AND  |
| Systemic Symptoms         | at least ONE of the following systemic symptoms: Fever (temperature $\geq 38^{\circ}\text{C}/\geq 100.4^{\circ}\text{F}$ ) or chills (of any duration, |

|                      |   |
|----------------------|---|
|                      | including $\leq$ 48 hours), fatigue, headache, myalgia, nasal congestion or rhinorrhea, new loss of taste or smell, sore throat, abdominal pain, diarrhea, nausea/vomiting, poor appetite/poor feeding; OR            |
| Respiratory symptoms | at least ONE of the following respiratory signs/symptoms: cough (of any duration, including $\leq$ 48 hours), shortness of breath or difficulty breathing (of any duration, including $\leq$ 48 hours). |

The date of documented CDC Case Definition of COVID-19 (case) will be the later date of ([1 systemic symptom reported, or respiratory symptom reported] and, [date of positive PCR test]). Specifically, the date of documented CDC Case Definition of COVID-19 will be the later date of the following two dates (date of positive PCR test, and the date of eligible symptom(s)), and the two dates should be within 14 days of each other.

- Date of positive PCR test,
- Date of eligible symptom(s), defined as earliest of
  - Respiratory symptom: earliest date of an eligible respiratory symptom is reported
  - Systemic symptoms: earliest date of the eligible systemic symptom is reported

The time to the first occurrence of CDC Case Definition of COVID-19 will be calculated as:

Time to the 1st occurrence of CDC Case Definition of COVID-19 = Date of documented CDC Case Definition of COVID-19 – Date of randomization + 1. (For Part 1, switch date of randomization to date of first injection).

Cases will be counted start 14 days after the 2nd injection, i.e. date of documented CDC Case Definition of COVID-19 - Date of the 2nd injection  $\geq$  14.

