### **6.5.2. Analysis Method**

The number and percentage of subjects who had an event (i.e. the first asymptomatic SARS-CoV-2 infection) will be summarized in the PP set for Efficacy.

The incidence rate will be provided by age and vaccination group, calculated as the number of cases divided by the total person-time. The 95% CI of the incidence rate will be calculated using the exact method (Poisson distribution) and adjusted by person-time.

Person-time is defined in Part 2 as the total time from randomization date to the date of event, last date of study participation, censoring time, or efficacy data cutoff date, whichever is earlier. For Part 1, switch randomization date to date of first injection.

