## **6.5. Efficacy Analysis**

Exploratory analyses of incidence rates in COVID-19, SARS-CoV-2 infection, and asymptomatic infection will be performed using mITT1 Set. The mITT1 Set for the long-term analysis will be used for the incidence rate analysis in the long term including both the blinded and open-label phases; the mITT1 Set for the booster dose analysis will be used for the incidence analysis in the booster dose phase, unless otherwise specified. Subjects will be included in the vaccination group as defined in Section 6.1. As protocol amendment 9 was implemented in October 2022, no surveillance was conducted thereafter, and, therefore, no incidence rates will be calculated after October 2022.

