### **6.5.2. Analysis Method**

The number and percentage of subjects who had an event will be summarized in the mITT1 Set for the long-term analysis and booster dose phase analysis

The incidence rate will be provided by age and vaccination group if applicable, calculated as the number of cases divided by the total person-time. The 95% CI of the incidence rate will be calculated using the exact method (Poisson distribution) and adjusted by person-time.

Person-time is defined as the total time from date of the 1st dose of each part to the date of event, dose date in next part, last date of study participation, censoring time, or efficacy data cutoff date, whichever is earlier.

Incidence rate will also be analyzed by time period or by calendar month.

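### In both SAPs the main incidence rates count cases from 14 days after Dose 2, Dose 1 or the booster but start person-time earlier, so the absolute rates are understated

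*SAP*

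**What the plan says.** The document holds two SAPs: one for Part 1 and the Part 2 blinded phase, and one for the Part 2 open-label phase, boosters and Part 3. Each has a Section 6.5.2 (Analysis Method).

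**Blinded-phase SAP**
- Section 6.5.2 gives the incidence rate as "calculated as the number of cases divided by the total person-time", with an exact Poisson interval.
- One definition of person-time serves every endpoint: "Person-time is defined in Part 2 as the total time from randomization date to the date of event". Part 1 uses the first injection instead.
- For SARS-CoV-2 infection (Section 6.5.1.1): "Cases will be counted starting 14 days after the second injection". For CDC-definition COVID-19 (Section 6.5.1.3): "Cases will be counted start 14 days after the 2nd injection". The asymptomatic and P301-definition endpoints follow the same rule.
- A parallel count runs from 14 days after Dose 1. Section 6.5 gives it its own population: "The mITT1 Set will be the primary analysis set used for efficacy analysis of efficacy endpoints starting from 14 days after first dose". The PP Set for Efficacy serves the Dose 2 count.
- Section 6.5.3 plans sensitivity analyses that count cases from randomization (Part 2) or first injection (Part 1). Section 6.5.1.4 adds a similar summary for the P301 definition.

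**Open-label and booster SAP**
- Section 6.5.2: "Person-time is defined as the total time from date of the 1st dose of each part to the date of event".
- Sections 6.5.1.1 to 6.5.1.4 count cases from 14 days after the second mRNA-1273 dose, or from 14 days after the booster. For infection there is also a summary from 14 days after the first dose.
- Section 6.5 states that "no incidence rates will be calculated after October 2022".

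**The concern.** A rate is interpretable when its numerator and denominator cover the same period at risk. Here the denominator opens on Day 1 while the numerator opens weeks later. The days between add person-time but cannot, by definition, add a case. Neither SAP moves the person-time start to the first countable day.

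Nor does either SAP say what happens to a child whose event falls before that day. The PP Set for Efficacy screens infection status at baseline only. A child infected on Day 20 can therefore remain in the set without being a countable case, and the text does not say whether that child's person-time stops, continues or is removed.

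What is at stake is the level of every main (non-sensitivity) incidence rate, and whether rates can be compared across age groups with different follow-up or between the primary-series and booster phases, which have different gaps.

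**Working it through.** The plan states no incidence rate, case total or person-time total, so there is no figure to reproduce. The check sizes the mismatch.

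**Inputs**
- Doses are "administered as 2 intramuscular (IM) injections, approximately 28 days apart for Part 1 and Part 2" (blinded-phase SAP, Section 4.1). Appendix E puts randomization and Dose 1 on Day 1 and Dose 2 on Day 29.
- Case windows open 14 days after Dose 2, Dose 1 or the booster.
- Follow-up T, in days from the person-time start, is assumed. Reference points come from the schedules: 56 (Day 57), 208 (Day 209, six months after Dose 2, when Section 4.4 makes under-6s eligible for unblinding), 393 (Day 394), and 180 and 365 days after a booster.

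**Gap**
- Dose 2 count: 28 + 14 = 42 days.
- Dose 1 or booster count: 14 days.

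**Uncountable share of person-time = gap / T**

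| Count | T (days) | Share |
|---|---|---|
| Dose 2 | 56 | 42/56 = 75% |
| Dose 2 | 208 | 42/208 = 20% |
| Dose 2 | 393 | 42/393 = 11% |
| Dose 1 | 208 | 14/208 = 7% |
| Booster | 180 | 14/180 = 8% |
| Booster | 365 | 14/365 = 4% |

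A Dose 2 given 7 or 21 days late widens the gap to 49 or 63 days, which is 24% or 30% of 208 days.

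**Constant-hazard check.** Take hazard λ = 100 per 1000 person-years (assumed), gap g, and person-time ending at any event.
- Expected cases per child: exp(−λg) − exp(−λT).
- Person-time as written: (1 − exp(−λT))/λ.
- Matched person-time: (exp(−λg) − exp(−λT))/λ.

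The matched rate returns 100 at every T. The rate as written is:
- Dose 2 count: 24.9 at 56 days, 79.3 at 208, 88.8 at 393.
- Dose 1 count: 93.1 at 208 days.
- Booster count: 92.0 at 180 days, 96.0 at 365.

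The simple gap/T shares are therefore accurate to about one percentage point at this hazard.

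**Interval.** The exact Poisson limits are limits on the count divided by person-time. Both limits shrink by the same factor as the rate.

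**Ratio between arms.** With equal follow-up in both arms, the model turns a true ratio of 0.500 into 0.501. With unequal follow-up of Tv (vaccine) and Tp (placebo), the ratio is multiplied by about [(Tv − 42)/Tv] / [(Tp − 42)/Tp]:
- 90 and 70 days: (48/90)/(28/70) = 1.33.
- 208 and 188 days: (166/208)/(146/188) = 1.03.

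**The case against.** The strongest reply is that nothing inferential rests on these rates. Incidence is secondary in the blinded phase. In the later phases it is exploratory under Sections 2.1, 2.2.4, 3.3.4 and 6.5 of the second SAP, although its Sections 6.5.1.1 to 6.5.1.4 keep the secondary label. The plan gives counts, percentages and a rate with an interval for each group. It specifies no rate ratio, efficacy estimate or test for incidence, and the multiplicity scheme covers immunogenicity only. All of this stands and limits the severity.

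A reader might infer that the mismatch biases a vaccine-to-placebo comparison. The documents do not support that. The blinded efficacy period ends under one rule for both arms, the unblinding eligibility in Section 4.4 does not depend on arm, and equal follow-up leaves a ratio almost unchanged. The factor of 1.33 needs follow-up that is both short and unequal, which is hypothetical; the same 20-day difference near 208 days gives 1.03.

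A second reply is that the time origin is explicit and that Section 6.5.3 already plans an analysis in which both counts start together. That is true, but the sensitivity analysis covers a different window and does not correct the main rates. Stating the origin openly does not make the uncountable days time at risk.

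**Conclusion.** The mismatch stands in the current text of both SAPs, and its direction is certain: the main absolute rates and their intervals are too low. The size is about gap/T, with T assumed, because the documents give no mean follow-up for incidence. At the reference points of 208 days for the primary series and 180 to 365 days for the booster, that is about 20% for the Dose 2 count, 7% for the Dose 1 count and 4% to 8% for the booster. Very short follow-up makes it larger.

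Two stronger readings should be set aside:
- One could combine the August 2021 enrolment dates in Appendix G of the second SAP with the 10 November 2021 snapshot. That gives 81 to 91 days of follow-up and a share of 46% to 52%. The snapshot is cited for the immunogenicity coprimary tests, however, not for incidence.
- One could infer that time after surveillance stopped enters the denominators, because the person-time end points in the second SAP do not name October 2022. Section 6.5 of that SAP already bars rates after that month, and Sections 2.2.4 and 3.3.4 agree. Only a wording gap remains.

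The analyses that count from randomization or first injection are not diluted, and immunobridging is untouched. This is a point that should be fixed, not one that threatens the trial's conclusions.

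**What to change.** In Section 6.5.2 of both SAPs, define person-time separately for each counting rule. Start it on the first day a case can be counted (14 days after Dose 2, Dose 1 or the booster), and include only children who are event-free and uncensored on that day. This also settles how earlier events are handled.

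Keep the randomization or first-injection start only for the analyses that count cases from that date: the sensitivity analyses in Section 6.5.3 and the added P301-definition summary in Section 6.5.1.4 of the blinded-phase SAP.

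As a minor consistency edit, name the October 2022 end of surveillance among the person-time end points in Section 6.5.2 of the second SAP, in line with its Section 6.5.

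The cost is SAP wording and a re-run of the incidence tables. No new data are needed.

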### **6.5.3 Sensitivity and Subgroup Analysis**

Sensitivity analysis for these efficacy endpoints will be performed with the same methods described above based on the FAS, mITT Set and mITT1 Set, with cases counted starting from date of first injection in Part 1 and starting from randomization in Part 2. A sensitivity analysis will be performed to include subjects with positive SARS-CoV-2 status at baseline.

In addition to the secondary efficacy endpoint COVID-19 (both CDC definition and P301 case definition) based on eligible symptoms and confirmed positive RT-PCR results (central lab or local diagnostic test) originally defined in section 6.5.1.3 and 6.5.1.4, a second set of COVID-19 (CDC definition and P301 case definition), considering both RT-PCR results and other non-RT-PCR test results including home antigen tests will also be derived, which may be considered as a sensitivity analysis of COVID-19 cases. For 6 to <12 years of age, the non-RT-PCR tests will be identified for associated sample collection dates on or after 01 Dec 2021 when home antigen tests started to become widely available, to be included in a sensitivity analysis of COVID-19 cases in the CSR. For 6 months to <2 years and 2 to <6 years of age groups, the non-RT-PCR tests will be identified in the entire study period for the sensitivity analysis for the EUA and CSR.

Subgroup analysis in Part 1 is not needed and it may be done for Part 2 (or Part 1 +Part 2).

## **6.6. Long-term Analysis (including Part 2 Open-Label Phase)**

Long-term Analysis will be described in a separate SAP.

## 6.7. Booster Dose Analysis

Booster Phase Analysis will be described in a separate SAP.

## 6.8. Exploratory Analysis

### 6.8.1. Exploratory Analysis of Immunogenicity

The below exploratory analyses of immunogenicity may be performed:

- The genetic and/or phenotypic relationships of isolated SARS-CoV-2 strains to the vaccine sequence.
- Descriptive summaries of the ratio or profile of specific S protein bAb relative to nAb in serum during the study. The analysis may not be included in the Clinical Study Report (CSR).
- Descriptive summaries of clinical profile and immunologic endpoints to characterize participants with SARS-CoV-2 infection during the study.
- Assess the SARS-CoV-2 S protein-specific T-cell responses in a subset of participants.
- Descriptive summaries of GM and GMFR of bAb levels against SARS-CoV-2 nucleocapsid protein (quantitative IgG) and % of participants with 2x, 3x and 4x rise of bAb relative to baseline)
- The seroresponse rate comparisons between children in P204 and young adults ( $\geq 18$  to 25 years of age) in P301 may be performed using the bAb and nAb measures based on assay-specific seroresponse definitions for select bAb or nAb.

### 6.8.2. SARS-CoV-2 Exposure and Symptoms

SARS-CoV-2 reported exposure history and symptoms assessment will be assessed during the study.

The number and percentage of subjects who had close contact with a person with SARS-CoV-2 infection or COVID-19, reasons for exposure, subjects with any symptoms of potential COVID-19, and subjects with each symptoms will be presented by visit, age and vaccination group as defined in [Section 6.1](#). Descriptive statistics will be provided for length of exposure in days by vaccination group.

In addition, the following listings will be provided for subjects infected by SARS-CoV-2:

- Serum bAb level against SARS-CoV-2
- Serum nAb value against SARS-CoV-2
- Solicited ARs
- Unsolicited AEs

## 6.9. Interim Analyses

Part 1: Interim analyses may be performed after all or a subset of participants (with immunogenicity samples collected for D1 and D57) have completed Day 57 within an age group in Part 1 (one optional interim analysis for each age group, 3 interim analyses total for the 3 age groups in Part 1). Analyses of safety and immunogenicity may be conducted at each interim analysis. Additional interim analysis of immunogenicity and safety may be performed after all or subset of participants who receive booster dose have completed BD-Day 29 after the booster dose in an age group.

Part 2: An interim analysis of immunogenicity and safety will be performed after all or a subset of participants have completed Day 57 (1 month after the second dose) in Part 1 or Part 2 within an age group. This interim analysis will be considered the primary analysis of immunogenicity for a given age group. Another interim analysis on safety may be performed after a different subset or all participants have completed Day 57 in an age group. Additional interim analysis of immunogenicity and safety may be performed after all or subset of participants who receive booster dose have completed BD-Day 29 after the booster dose in an age group.

Part 3: An interim analysis of immunogenicity and safety will be performed after all or a subset of participants have completed Day 57 (1 month after the second dose) in Part 3 within an age group. This interim analysis will be considered the primary analysis of immunogenicity for the primary series in a given age group. A second interim analysis of immunogenicity and safety will be performed after all or a subset of participants have completed Day 177/BD-Day 29 (1 month after third dose).

An interim analysis of safety for mRNA-1273.214 booster may be performed after all or a subset of mRNA-1273.214 recipients have completed 6 months of follow-up after the booster dose.

The final analysis of all endpoints will be performed after all participants have completed all planned study procedures and after the database is cleaned and locked. Results of this analysis will be presented in an end of study CSR, including individual listings.

## **6.10. Data Safety Monitoring Board**

Safety oversight will be under the direction of a DSMB composed of external independent consultants with relevant expertise. Members of the DSMB will be independent from study conduct and free of conflict of interest. The DSMB will meet at pre-specified timepoints during the study to assess safety throughout study conduct. For the 6 years to < 12 years age group, the DSMB will review cumulative safety data for approximately 300 participants enrolled at the selected dose level in Part 1 before enrollment begins in Part 2. For both the middle age group (2 years to < 6 years) and the youngest age group (6 months to < 2 years) the DSMB will review cumulative safety data in both younger age groups (2 years to < 6 years; 6 months to < 2 years) combined and at all dose levels administered in Part 1 before start of Part 2 (blinded phase) for each age group. The DSMB will operate under the rules of an approved charter that will be written and reviewed at the organizational meeting of the DSMB. Details regarding the DSMB composition, responsibilities, procedures, and frequency of data review will be defined in its charter.

If any of the study pause rules, described in protocol section 6.4, are met, the Sponsor will immediately suspend further enrollment and/or study dosing and the DSMB will convene on an ad hoc basis. The DSMB will review all available unblinded study data (as applicable) to help adjudicate any potential study pauses and make recommendations on further study conduct, including requesting additional information, recommending stopping the study, recommending changes to study conduct and/or the protocol, or recommending additional operational considerations due to safety issues that arise during the study.

The Cardiac Event Adjudication Committee (CEAC) consisting of pediatric and adult cardiologists will review suspected cases of myocarditis, pericarditis, or myopericarditis to determine if they meet CDC criteria of “probable” or “confirmed” event, and to assess severity and enable the DSMB to make recommendations to the Sponsor to continue vaccine dosing. The CEAC will operate under the rules of an approved charter that will be written and reviewed at the organizational meeting of the CEAC. Details regarding the CEAC composition, responsibilities, procedures, and frequency of data review will be defined in its charter.

